### Performance evaluation criterias

| Extracorporeal life support system with pulmonary and / or heart failure |
|---|
| Primary results  |

|                          |   |
|--------------------------|---|
| 1                 | Cytokine response [Time: 24-48 hours]

The level of pro- and anti-inflammatory cytokines (IL-1, IL-6, IL-8, IL-10, tumor alpha-factor) before the implantation, 2 hours after the start of ECMO support, explantation of ECMO, 24 hours after explantation of ECMO.     |
| 2                 | SOFA-Score [Time Frame: 24, 48, 72 hours]

Sequential Organ Failure Assessment Score at 24, 48, 72 h (values from 6 to 24, where the higher values explain higher disease severity)   |
| 3                 | Difference of mean arterial pressure [Time Frame: 24, 48, 72 hours]

Comparison of mean arterial pressure at 24, 48, 72 hours between between two interventions (CytoSorb and Jafron)   |
| 4                 | Difference of CVP [Time Frame: 24, 48, 72 hours]

Comparison of CVP at 24, 48, 72 hours between between two interventions (CytoSorb and Jafron)   |
| 5                 | Serum lactate [ Time Frame: 24, 48, 72 hours ]

Level of serum lactate at 24, 48, 72 h  |
| 6                 | 
 
Days on ventilator, vasopressor and renal replacement therapy [ Time Frame: until day 30 post-surgery ]
 

Total days on ventilator, vasopressor and renal replacement therapy within 30 days post-surgery will be assessed |
| 7                 | Doses of vasopressors and / or inotropes ( $\mu\text{g} / \text{h} / \text{kg}$ bodyweight) [Time: first 72 hours]  |
| Secondary results |   |
| 1                 | Inflammatory response - The level of C-reactive protein (CRP) [Time: 24-48 hours]

The level of C-reactive protein (CRP) before the start of ECMO, 2 hours after the implantation of ECMO, during ECMO, 24 hours after ECMO explantation.                        |
| 2                 | Inflammatory response - The level of leukocytes [Time: 24-48 hours]

The level of leukocytes before the start of ECMO, 2 hours after the implantation of ECMO, during ECMO, 24 hours after ECMO explantation.   |
| 3                 | Inflammatory response - The level of procalcitonin [Time: 24-48 hours]

The level of procalcitonin before the start of ECMO, 2 hours after the implantation of ECMO, during ECMO, 24 hours after ECMO explantation.   |
| 4                 | Level of leukocyte [Time: 24-48 hours]

Level of leukocyte cells in the bloodstream at 24, 48 hours.  |

|                          |  |
|--------------------------|--|
| 5                 | Application and dosage of vasopressors [Deadline: first 48 hours]
Incidence of application and level of dosage of vasopressors on days 2 and 3 after surgery; |
| 6                 | Application and dosage of inotropes [Deadline: first 48 hours]
Incidence of application and level of dosage of inotropes on days 2 and 3 after surgery;       |
| Long-term results |  |
| 1                 | Length of stay in the intensive care unit [Duration: first 48 hours]   |
| 2                 | Length of hospital stay [Term: up to 1 month];   |
| 3                 | 30 day survival rate.  |

| Patients with left ventricular assist device implantation |  |
|--|--|
| Primary results   |  |
| 1   | Difference of Cytokine response [Time: 24-48 hours]
Level of pro- and anti-inflammatory cytokines (IL-1, IL-6, IL-8, IL-10, tumor necrosis factor-alfa, procalcitonin)  |
| 2   | Doses of vasopressors and / or inotropes ( $\mu$ g / h / kg bodyweight)
[Deadline: first 72 hours]  |
| 3   | Renal function [Time: first 72 hours] creatinine level   |
| 4   | Lactate level [Time: first 72 hours]   |
| Secondary results   |  |
| 1   | Inflammatory response - The level of C-reactive protein (CRP) [Time: 24-48 hours]
The level of C-reactive protein (CRP) before the start of the operation, 2 hours after the start of the operation, when the operation is turned off, 24 hours after the shutdown of the operation |
| 2   | Inflammatory response - The level of leukocytes [Time: 24-48 hours]
The level of leukocytes before the start of the operation, 2 hours after the start of the operation, when the operation is turned off, 24 hours after the shutdown of the operation                             |
| 3   | Inflammatory response - The level of procalcitonin [Time: 24-48 hours]
The level of procalcitonin before the start of the operation, 2 hours after the start of the operation, when the operation is turned off, 24 hours after the shutdown of the operation                       |

|                          |  |
|--------------------------|--|
| 4                 | Application and dosage of vasopressors [Deadline: first 48 hours]
Incidence of application and level of dosage of vasopressors on days 2 and 3 after surgery; |
| 5                 | Application and dosage of inotropes [Deadline: first 48 hours]
Incidence of application and level of dosage of inotropes on days 2 and 3 after surgery;       |
| Long-term results |  |
| 1                 | Length of stay in the intensive care unit [Duration: first 48 hours]   |
| 2                 | Length of hospital stay [Term: up to 1 month];   |
| 3                 | 30 day survival rate.  |

| For operations with prolonged cardio pulmonary bypass, hypothermia and circulatory arrest |  |
|--|--|
| Primary results   |  |
| 1   | Cytokine response [Time: 24-48 hours]
Difference of Cytokine response [Time: 24-48 hours]
Level of pro- and anti-inflammatory cytokines (IL-1, IL-6, IL-8, IL-10, tumor necrosis factor-alfa, procalcitonin, C-reactive protein) |
| 2   | SOFA-Score [Time Frame: 24, 48, 72 hours]
Sequential Organ Failure Assessment Score at 24, 48, 72 h (values from 6 to 24, where the higher values explain higher disease severity)  |
| 3   | Difference of mean arterial pressure [Time Frame: 24, 48, 72 hours]
Comparison of mean arterial pressure at 24, 48, 72 hours between between two interventions (CytoSorb and Jaftron)   |
| 4   | Difference of CVP [Time Frame: 24, 48, 72 hours]
Comparison of mean arterial pressure at 24, 48, 72 hours between between two interventions (CytoSorb and Jaftron)  |
| 5   | Level of Serum lactate [ Time Frame: 24, 48, 72 hours ]
Comparison of mean arterial pressure at 24, 48, 72 hours between between two interventions (CytoSorb and Jaftron)   |
| Secondary results   |  |
| 1   | Inflammatory response - The level of C-reactive protein (CRP) [Time: 24-48 hours]
The level of C-reactive protein (CRP) before the cardiopulmonary bypass 2 hours   |

|                          |  |
|--------------------------|--|
|                          | after the cardiopulmonary bypass, when the cardiopulmonary bypass is turned off, 24 hours after the cardiopulmonary bypass.  |
| 2                 | Inflammatory response - The level of leukocytes [Time: 24-48 hours]
The level of leukocytes before the cardiopulmonary bypass 2 hours after the cardiopulmonary bypass, when the cardiopulmonary bypass is turned off, 24 hours after the cardiopulmonary bypass.       |
| 3                 | Inflammatory response - The level of procalcitonin [Time: 24-48 hours]
The level of procalcitonin before the cardiopulmonary bypass 2 hours after the cardiopulmonary bypass, when the cardiopulmonary bypass is turned off, 24 hours after the cardiopulmonary bypass. |
| 4                 | Application and dosage of vasopressors [Deadline: first 48 hours]
Incidence of application and level of dosage of vasopressors on days 2 and 3 after surgery;   |
| 5                 | Application and dosage of inotropes [Deadline: first 48 hours]
Incidence of application and level of dosage of inotropes on days 2 and 3 after surgery;   |
| Long-term results |  |
| 1                 | Length of stay in the intensive care unit [Duration: first 48 hours]   |
| 2                 | Length of hospital stay [Term: up to 1 month];   |
| 3                 | 30 day survival rate.  |

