#### **4. Research methods and ethical issues.**

All patients admitted to Non-profit JSC “NRCCS” who meet the study criteria (patients on an extracorporeal life support system, mechanical circulatory support, surgery on the aortic arch) will be included in the study after obtaining a signed informed consent. Participants will be randomized into 2 groups in a 1: 1 division.

**Intervention team # 1** using an extracorporeal hemoperfusion device Jaftron (Zhuhai Jaftron Biomedical, China) (50 patients) in subgroups: A (n = 10) - patients on extracorporeal life support systems with heart failure; B (n = 10) - patients on extracorporeal life support systems with pulmonary failure; C (n = 5) - patients with implantation of a left ventricular accessory device; D (n = 25) - during operations with prolonged artificial circulation, hypothermia and circulatory arrest.

**Intervention team # 2** using extracorporeal cytokine, CytoSorb (CytoSorbents Corporation, Monmouth Junction, NJ, USA) (50 patients) in subgroups: A (n = 10) - patients on extracorporeal life support systems in heart failure; B (n = 10) - patients on extracorporeal life support systems with pulmonary failure; C (n = 5) - patients with implantation of a left ventricular accessory device; D (n = 25) - during operations with prolonged artificial circulation, hypothermia and circulatory arrest.

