#### **Study design.**

Study type: interventional (clinical study)

Set of participants: 100 participants

Distribution: randomized

Interventional model: parallel

Masking: no

Primary Goal: Treatment

| Intervention team (1 group)  | Intervention / treatment (device)  |
|--|--|
| Extracorporeal hemoperfusion device will be installed in the device of the extracorporeal life support system for heart failure...
(10 patients)        | HA330 - Jafron Biomedical Co., Ltd., China
- extracorporeal hemocorrection, which is based on the removal of cytokines from whole blood by sorption on a special hemoabsorbent due to the peculiarities of its porous structure and inner surface, which is indicated in conditions where cytokine levels are extremely elevated. |
| Extracorporeal hemoperfusion device will be installed in the device of the extracorporeal life support system for pulmonary failure
(10 patients).      | HA330 - Jafron Biomedical Co., Ltd., China
- extracorporeal hemocorrection, which is based on the removal of cytokines from whole blood by sorption on a special hemoabsorbent due to the peculiarities of its porous structure and inner surface, which is indicated in conditions where cytokine levels are extremely elevated. |
| An extracorporeal hemoperfusion device will be installed in patients before / during the implantation of a left ventricular assist device
(5 patients). | HA330 - Jafron Biomedical Co., Ltd., China
- extracorporeal hemocorrection, which is based on the removal of cytokines from whole blood by sorption on a special hemoabsorbent due to the peculiarities of its porous structure and inner surface, which is indicated in conditions where cytokine levels are extremely elevated. |
| An extracorporeal hemoperfusion device will  | HA330 - Jafron Biomedical Co., Ltd., China   |

|   |  |
|---|--|
| be installed in patients during operations with prolonged cardiopulmonary bypass, hypothermia and circulatory arrest. (25 patients).  | - extracorporeal hemocorrection, which is based on the removal of cytokines from whole blood by sorption on a special hemoadsorbent due to the peculiarities of its porous structure and inner surface, which is indicated in conditions where cytokine levels are extremely elevated. |
| Intervention team (2 groups)   |  |

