### Statistical research

- 1) statistical data processing
- 2) comparison and analysis of initial data

After data acquisition, statistical analysis will be performed using SPSS Statistics version 22. For quantitative data, the nonparametric Mann-Whitney U test and parametric t-test will be performed, and for qualitative studies, the nonparametric Fisher's exact test and the parametric  $\chi^2$  test will be performed. Also, logistic regression for categorical outcomes and survival analyzes (non-parametric Kaplan-Meyer and parametric Cox regression) will be performed.

**Age:** 18 years and older

**Gender:** All

**Inclusion of healthy volunteers:** Not

| Groups  | Inclusion criteria   | Exclusion criteria  |
|--|---|--|
| Patients on an extracorporeal life support system with heart failure                             | 
 
• Implantation of intravenous ECMO
 
• Hemodynamic support with vasopressors and / or tonics;
 
• Procalcitonin level <math>\geq 1</math> ng / ml;
 
• Invasive hemodynamic monitoring;
 
• Written informed consent.
 
   | 
 
• Age less than 18 years old
 
• Terminal hepatic or renal failure just before the procedure
 
• Patient's written refusal to participate in the study
 
 |
| Patients on an extracorporeal life support system with pulmonary failure                         | 
 
• IV ECMO implantation
 
• High levels of venous and arterial CO2 (CO2 > 50 mmHg),
 
• Low paO2, SvO2, SpO2.
 
• Invasive hemodynamic monitoring;
 
• Written informed consent.
 
                                     | 
 
• Age less than 18 years old
 
• Terminal hepatic or renal failure just before the procedure
 
• Patient's written refusal to participate in the study
 
 |

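### Two ECMO cohorts with different entry criteria share one list of primary results, and the named tests for quantitative outcomes carry no cohort term, so a pooled device comparison would lose power if the cohorts differ

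*Combined protocol and SAP*

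**What the plan says.** Section 4, Research methods and ethical issues, states "Participants will be randomized into 2 groups in a 1: 1 division" and then lists the same four subgroups with the same counts in each arm. Two of them are ECMO cohorts: "A (n = 10) - patients on extracorporeal life support systems with heart failure" and "B (n = 10) - patients on extracorporeal life support systems with pulmonary failure". C (LVAD) has 5 per arm and D (prolonged bypass) has 25. No stratification or blocking is described.

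Under Performance evaluation criterias, LVAD and prolonged-bypass patients each have their own outcome table. Cohorts A and B share one, headed "Extracorporeal life support system with pulmonary and / or heart failure", with a single list of seven primary results. Row 7 is "Doses of vasopressors and / or inotropes" over the first 72 hours.

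The eligibility table under Statistical research separates the two cohorts. A must have "Hemodynamic support with vasopressors and / or tonics" and procalcitonin of at least 1 ng/ml. B has neither criterion; its own criteria concern CO2 and oxygenation.

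The same section says: "For quantitative data, the nonparametric Mann-Whitney U test and parametric t-test will be performed". Logistic and Cox models are named for categorical and survival outcomes, without covariates. Nothing names a cohort factor or a baseline adjustment for a quantitative outcome.

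**The concern.** Support with vasopressors or similar drugs is an entry condition for half of the ECMO patients and not for the other half, and the dose of those drugs is a primary result for all of them. A gap between A and B on that row is plausible whichever device is used. The other primary rows (cytokines, SOFA, arterial and venous pressure, lactate) may differ too, though the documents give no figures.

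If the 40 ECMO patients are compared as 20 v 20 with a plain two-sample test, the A-B gap enters the analysis as unexplained variation. With only 20 per arm, a real difference between devices could be missed for a reason that a cohort term would remove. Because the plan does not say whether A and B are pooled or split, and the study is unmasked, that choice could also be made after the data are seen.

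**Working it through.** **Figures in the plan.** There is no power calculation to reproduce: no alpha, SD, effect size or power is given. The counts agree: 10 + 10 + 5 + 25 = 50 per arm, 2 × 50 = 100, matching "Set of participants: 100 participants". The ECMO part is 4 × 10 = 40, or 20 per arm.

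**Assumptions, not in the documents.** Two-sided 5% level; normal data; the same within-cohort SD, *s*, in A and B; device effect 1 *s*; A-B gap of *d* within-cohort SDs, with *d* from 0 to 3.

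**Case 1: the listed counts are delivered (10 A and 10 B per arm).** The gap cancels in the difference between arms, so the true SE is *s*√(2/20) = 0.316 *s* for every *d*. The plain t-test still includes the gap in its variance: each arm gains a sum of squares of 20 × (*d*/2)² = 5*d*² on 19 degrees of freedom. The reported SE is therefore *s*√[(2/20)(1 + 5*d*²/19)].

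**Case 2: 20 A and 20 B, split 20:20 between arms without regard to cohort.** The cohort mix now varies by chance. The variance contributed by the gap is 40 × (*d*/2)²/39 = 10*d*²/39, so the true SE is *s*√[(2/20)(1 + 10*d*²/39)]. Simulation shows that the t-test reports this SE correctly (0.355 *s* reported against 0.354 *s* true at *d* = 1; 0.450 against 0.449 at *d* = 2).

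The SEs below are in units of *s*, from the formulas. Power and false-positive rates are from simulation.

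| | *d* = 0.5 | *d* = 1 | *d* = 2 | *d* = 3 |
|---|---|---|---|---|
| Case 1: reported SE (true 0.316) | 0.326 | 0.355 | 0.453 | 0.580 |
| Case 1: ratio of reported to true SE | 1.03 | 1.12 | 1.43 | 1.84 |
| Case 1: false-positive rate, plain t-test | 4.4% | 2.9% | 0.5% | 0.05% |
| Case 1: power, plain t-test | 86% | 81% | 61% | 30% |
| Case 1: power, with cohort term | 87% | 87% | 87% | 87% |
| Case 2: true SE | 0.326 | 0.354 | 0.450 | 0.575 |
| Case 2: false-positive rate, plain t-test | 5% | 5% | 5% | 5% |
| Case 2: power, plain t-test | 85% | 78% | 58% | 39% |
| Case 2: power, with cohort term | 86% | 86% | 86% | 86% |

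The Mann-Whitney test follows the same pattern in case 1: power 78%, 54% and 23% at *d* = 1, 2 and 3. A smaller assumed effect of 0.9 *s* gives t-test power of 77%, 72%, 49% and 21% in case 1, against 79% adjusted. At *d* = 0 the plain and adjusted analyses agree (both about 87% in case 1 at effect 1 *s*).

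**Which case applies?** Under simple 1:1 allocation, all the listed counts arise together with probability [C(20,10)/2²⁰]² × [C(10,5)/2¹⁰] × [C(50,25)/2⁵⁰] = 0.1762² × 0.2461 × 0.1123 ≈ 0.0009. If the totals are forced to 50:50, it is C(20,10)² × C(10,5) × C(50,25)/C(100,50) ≈ 0.011. A cohort of 20 splits 13:7 or worse 26% of the time. If A split 13:7 and B 10:10, the arms would hold 13/23 = 0.565 and 7/17 = 0.412 A patients, which moves the unadjusted difference in that one trial by about 0.15 of the A-B gap.

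**The case against.** The strongest objection is that pooling is inferred. The shared heading can be read as one list of outcomes serving two cohorts. Section 4 and the Study design table keep A and B apart, as does the eligibility table. In the plan of implementation (section 8), items 4.1-4.3 collect data for pulmonary-failure ECMO and items 4.4-4.6 for heart-failure ECMO, with vasopressor dose in each set. If A and B are analysed separately, the 20 v 20 figures do not apply. This stands: a reader might infer that the plan has chosen a pooled analysis, but the documents do not say so. Separate 10 v 10 tests would, however, have only about 56% power at an effect of 1 SD, so splitting is not a free alternative if one device effect is wanted.

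A reader might also infer that the comparison both loses precision and reports wrong error bars. These are alternatives. In case 1 the error bars are too wide and the true precision is unchanged; in case 2 precision is lost and the error bars are valid.

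Nor would it be right to infer that an arm holding more A patients makes the result biased or the test too liberal. Under random allocation such imbalance is noise, and the plain test's error rate already allows for it.

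Finally, the equal counts suggest that allocation within cohort may be intended. The small probabilities above show that simple allocation would not deliver those counts; they do not show that simple allocation is planned.

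The size of the loss is also uncertain. Entry to A sets no minimum dose, and B patients may be on vasopressors. Doses may be zero for some patients, so normal data with equal SDs are only a working approximation.

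**Conclusion.** The point holds conditionally. Two cohorts with different entry criteria share one set of primary results, the named tests for quantitative outcomes ignore cohort, and the plan does not state whether A and B are pooled or whether allocation is stratified. If they are pooled and differ, power falls under either form of allocation. Under the assumptions above, the loss is 1 to 2 percentage points at a gap of 0.5 SD, about 6 to 8 at 1 SD, and more than 25 at 2 SD. The true gap is not in the documents, so the size cannot be fixed more closely. The harm is a missed device difference; it is neither systematic bias nor an excess of false positives. A better analysis is available at almost no cost, so the change should be made.

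**What to change.** - **Section 4, Research methods and ethical issues:** state that patients are randomised 1:1 within each of cohorts A, B, C and D in permuted blocks, so that the listed counts are delivered.
- **Statistical research:** state that the devices are compared on the ECMO table's quantitative outcomes with an analysis stratified by cohort, in place of the plain t-test or Mann-Whitney test. Use a linear model with an A/B term, or the van Elteren test where normality is doubtful, as it may be for doses.
- **Same section:** stratify by cohort any logistic or Cox model that pools cohorts.
- **Reporting:** give A and B separately as supportive 10 v 10 results.

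This takes a few sentences and needs no extra patients or data. The cohort term uses about one degree of freedom, and almost nothing is lost if A and B do not differ.

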#### **Retrospective analysis of patients who received a fully artificial heart.**

The duration of the intervention in each group will be 72 hours. Each Jaftron / CytoSorb Removal Column can be used within 24 hours, so all patients in 2 groups use 3 filters during the study.

Researchers will collect demographic, clinical and laboratory data from patients before, during and after surgery.

The incidence of early cellular or humoral rejection, the duration of ventilation, intensive care and hospital stay, the use of vasopressors and inotropes in the perioperative period, and the incidence of perioperative complications and survivals will be documented.

The level of cytokines (IL-1, IL-6, IL-8, IL-10, tumor necrosis factor alpha) and complements will be determined before, during and after the use of the extracorporeal life support system for heart and pulmonary failure; surgery on the aortic arch, patients on mechanical circulatory support, if investigators find a corresponding difference between the two groups in terms of clinical variables.

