| Extracorporeal hemoperfusion device will be installed in the device of the extracorporeal life support system for heart failure.

(10 patients)                           | CytoSorb (CytoSorbents Corp., USA) - an extracorporeal cytokine adsorber is a biocompatible polymer with high adsorption capacity, which is indicated in conditions where cytokine levels are extremely elevated.  |
| Extracorporeal hemoperfusion device will be installed in the device of the extracorporeal life support system for pulmonary failure.

(10 patients)                       | CytoSorb (CytoSorbents Corp., USA) - an extracorporeal cytokine adsorber is a biocompatible polymer with high adsorption capacity, which is indicated in conditions where cytokine levels are extremely elevated.  |
| An extracorporeal hemoperfusion device will be installed in patients before / during the implantation of a left ventricular assist device

(5 patients)                   | CytoSorb (CytoSorbents Corp., USA) - an extracorporeal cytokine adsorber is a biocompatible polymer with high adsorption capacity, which is indicated in conditions where cytokine levels are extremely elevated.  |
| An extracorporeal hemoperfusion device will be installed in patients during operations with prolonged cardiopulmonary bypass, hypothermia and circulatory arrest. (25 patients) | CytoSorb (CytoSorbents Corp., USA) - an extracorporeal cytokine adsorber is a biocompatible polymer with high adsorption capacity, which is indicated in conditions where cytokine levels are extremely elevated.  |

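### Section 4 makes the primary cytokine assay conditional on a clinical difference, against the outcome tables and work plan; in the ECMO block the draw list does not fit its 24-48 h label if the 72 h course is completed in the circuit

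*Combined protocol and SAP*

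**What the plan says.** **Whether cytokines are assayed.** The tables under Performance evaluation criterias put cytokine response first among the primary results for ECMO, for LVAD implantation and for prolonged bypass, with no condition. The work plan (section 8, items 4.1, 4.4, 4.7 and 4.10) schedules cytokine blood sampling in the same populations, also without condition. Section 4, in the text below the artificial-heart subheading, says cytokine and complement levels "will be determined before, during and after the use of the extracorporeal life support system for heart and pulmonary failure". It extends this to aortic arch surgery and mechanical circulatory support, and ends the sentence with "if investigators find a corresponding difference between the two groups in terms of clinical variables".

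**When, in ECMO patients.** Primary result 1 is labelled 24-48 hours, and nothing says what the hours are counted from. The draws are "before the implantation, 2 hours after the start of ECMO support, explantation of ECMO, 24 hours after explantation of ECMO". Section 4 also states "The duration of the intervention in each group will be 72 hours" and, because one column serves for 24 h, "so all patients in 2 groups use 3 filters during the study". The Study design table puts the adsorber in the ECMO circuit: "Extracorporeal hemoperfusion device will be installed in the device of the extracorporeal life support system for heart failure". The entry for pulmonary failure is equivalent, and both device groups have the same entries.

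**Neighbouring ECMO outcomes.** Another primary result is "Sequential Organ Failure Assessment Score at 24, 48, 72 h". Mean arterial pressure, CVP and lactate use the same hours, again without a time zero. The secondary CRP, leukocyte and procalcitonin rows carry the 24-48 h label with event-tied draws and one untimed draw on support, for example "The level of leukocytes before the start of ECMO, 2 hours after the implantation of ECMO, during ECMO, 24 hours after ECMO explantation". Only secondary row 4, a second leukocyte row, fixes 24 and 48 h.

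**The concern.** Two things do not fit together.

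First, a primary outcome should be available in every randomised patient whatever the other results show. If section 4 is followed, cytokines are assayed only after a clinical difference between the groups has been found. The clinical variables, the size of difference and the time of that look are not stated. A neutral clinical result would leave the outcome empty. A positive one would give cytokine results selected on outcomes likely to be correlated with them.

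Second, in the ECMO block the label promises values at 24-48 h, but after the 2 h draw sampling follows explantation, whose timing is decided after randomisation in an unmasked trial. Patients who die on support have no post-explantation draw. The Statistical research section names no primary time point and gives no rule for variable sampling times or for deaths.

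**Working it through.** **1. Plan's own figure.** 3 filters x 24 h = 72 h, so the stated course and filter count agree with each other.

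**2. Patients concerned.** The ECMO subgroups are A and B in each arm: 4 x 10 = 40. The others are LVAD 2 x 5 = 10 and prolonged bypass 2 x 25 = 50, so 60. The sentence with the condition names all these populations: up to 40 + 60 = 100.

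**3. The condition, side by side.**
- Outcome tables: cytokine level is primary result 1 in all three blocks, unconditional.
- Work plan: cytokine blood sampling in all populations, unconditional.
- Section 4: levels determined if a clinical difference is found.

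One could try to harmonise these by sampling everyone and assaying only if the condition is met. The work plan would then be satisfied, but the primary result would still be missing whenever it is not met.

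**4. ECMO draw times.** Let E = hours from ECMO start to explantation and s = hours from ECMO start to adsorber start (s at least 0, because the device sits in that circuit). Draws after implantation are at 2, E and E + 24. A full course in the circuit requires E of at least 72 + s.

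| Clock | 2 h draw | Explantation | 24 h later | Draws at 24-48 h |
|---|---|---|---|---|
| ECMO start | 2 | at least 72 | at least 96 | 0 of 4 |
| Adsorber start | 2 - s, at most 2 | at least 72 | at least 96 | 0 of 4 |
| Explantation | 2 - E, negative | 0 | 24 | 1 of 4, lower edge |

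The pre-implantation draw is before zero on every clock. Counted from the end of the adsorber course, another possible zero, a draw falls in the window only if ECMO ends 0 to 48 h after the course.

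**5. Shorter ECMO, counted from ECMO start.** E itself lies in the window for E = 24 to 48, and E + 24 does for E up to 24. So a draw falls in the window for E up to 48, but the 72 h course is then not completed in that circuit. For E = 49 to 71 none does.

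**6. Draws while the adsorber runs** (ECMO continuing past the course). With s below 2, only the 2 h draw; with s above 2, none.

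**7. Common time.** The 2 h draw is common on the ECMO clock only, and if s exceeds 2 it precedes treatment. The documents do not state s, nor when randomisation falls relative to ECMO start. The later draws vary between patients. With assumed explantation at 72 h or 168 h, they fall at 72 and 96 h, or at 168 and 192 h, from ECMO start.

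**The case against.** The strongest reply on the condition is that it is an outlier in one badly built sentence, contradicted by every outcome block and by four work-plan items. That stands. A reader might infer that cytokines will not be measured unless clinical results differ. The documents do not support this, because it follows only if section 4 overrides the other texts. What is supported is a conflict that must be settled.

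On timing, the zero-draw result needs the 72 h course to be completed in the ECMO circuit. Section 4 applies 72 h and three filters to every patient, including those whose device is used during an operation, so the sentence may be generic. The number of ECMO patients who will complete the course there is not given. The bracketed times are also loose elsewhere: length of intensive care stay carries a 48 h limit. So the label mismatch alone is largely editorial. What survives is the sampling schedule: correcting the label would still leave no value shown to be at a common time after treatment starts.

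A reader might also infer that the event-tied draws bias the comparison. The documents do not show it. Assignment is 1:1, and if the devices do not differ in their effect on ECMO duration or survival, the cost is precision. Sampling around explantation is also a legitimate design, so those draws need not be demoted.

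The untimed mention of measurement during support does not settle the matter, since the 2 h draw could satisfy it.

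**Conclusion.** The point holds in two parts and should be corrected.

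(a) The condition in section 4 conflicts with the outcome tables and the work plan. Taken as written, it makes the availability of a primary outcome depend on other results, potentially in all 100 patients.

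(b) In up to 40 ECMO patients, primary result 1 has no time zero. With a full course in the circuit, 0 of 4 listed draws fall at 24-48 h from ECMO or adsorber start. If ECMO lasts 48 h or less, or hours are counted from explantation, a draw falls in the window or on its edge. A late difference between arms would be hard to interpret if the devices affect ECMO duration or survival, since it could reflect when patients came off support or who survived.

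Part (b) rests on reading the 72 h course and its location literally. The documents give no ECMO durations, adsorber start times or death rates on support for this trial, so the loss of precision cannot be sized.

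**What to change.** - Remove the condition in section 4, so that cytokines are assayed in all patients as the outcome tables require.
- State one time zero for the ECMO outcomes, and reconcile the 24-48 h label, the draw list and the 72 h course.
- Add cytokine draws at 24 and 48 h from that zero, hours already used for other outcomes in these patients, with a baseline before the adsorber starts.
- Pre-state how deaths before those times are handled and what the rule estimates. Ranking deaths worst gives a composite of cytokine level and death; comparing survivors only leaves selection by survival.
- The explantation and post-explantation draws can stay; whether they remain primary is the sponsor's choice.

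**Cost.** A protocol amendment and two extra samples per ECMO patient, or three if the pre-implantation draw cannot serve as the pre-adsorber baseline: 40 x 2 = 80 to 40 x 3 = 120 samples at most. With five cytokines that is 400 to 600 results. If assays are now conditional, removing the condition also commits the existing ECMO draws, 40 x 4 x 5 = 800 results, so about 1,200 to 1,400 in total for ECMO. It commits the assays in the other 60 patients too. Their primary cytokine rows list no draw times, so that part cannot be costed from the documents.
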